6.5.1.3.4 Mandatory dose modifications and recommended clinical management guidelines for skin rash

Guidelines for dose modification and management of skin rash considered to be related to study treatment by the investigator are provided in [Table 6-9](#).

Table 6-9 Mandatory dose modifications and recommended clinical management guidelines for rash

Rash Events (NCI-CTCAE v4.03)		
Grade	Recommended adverse event management guidelines	Mandatory dose modification requirements
Grade 1: Rash covering < 10% body surface area	
 Initiate prophylactic and symptomatic treatment measures. Consider use of topical corticosteroids or urea containing creams in combination with oral antipruritics or moderate strength topical steroid (hydrocortisone 2.5% cream or fluticasone propionate 0.5% cream) Reassess after 2 weeks 	
 Continue, dabrafenib and trametinib at the same dose.
Grade 2: 10-30% of body surface area	
 If tolerable, as per Grade 1 If intolerable, initiate systemic steroids (0.5 to 1 mg/kg/day prednisone or equivalents) If symptoms persist or recur consider skin biopsy. 	
 If tolerable, continue dabrafenib and trametinib at the same dose. If intolerable: 1st occurrence 
 Interrupt, dabrafenib and trametinib until \leq Grade 1, and then reinstate reduce dabrafenib and trametinib to the next dose level per Table 6-5. Re-escalation of the subject's dose is recommended if criteria in Section 6.5.1.2 are met AE resolution to \leq Grade 1 or baseline must occur within a period of 4 weeks since a Grade 2 event has been identified
Grade 3: More than 30% of body surface area	
Obtain a skin biopsy and dermatology consult.
 
Initiate therapy with high dose steroids (1 to 2 mg/kg/d prednisone or equivalents)
	
 1st occurrence 
 Interrupt dabrafenib and trametinib until \leq Grade 1, and reduce dabrafenib and trametinib to the next dose level per Table 6-5. Re-escalation of the subject's dose is recommended if criteria in Section 6.5.1.2 are met AE resolution to \leq Grade 1 or baseline must occur within a period of 4 weeks since a grade 3 event has been identified 2nd occurrence 
 Interrupt dabrafenib and trametinib until \leq Grade 1 or baseline. Once recovered, reduce dabrafenib and trametinib to the next dose level per Table 6-5. Re-escalation of the subject's dose is recommended if criteria in Section 6.5.1.2 are met 3rd occurrence 
 Interrupt dabrafenib and trametinib until \leq Grade 1 or baseline. Once recovered, reduce dabrafenib and trametinib to the next dose level per Table 6-5. Re-escalation of the subject's dose is recommended if criteria in Section 6.5.1.2 are met

Rash Events (NCI-CTCAE v4.03)		
Grade	Recommended adverse event management guidelines	Mandatory dose modification requirements
		4th occurrence 
 Permanently discontinue dabrafenib and trametinib.
Grade 4: Life-threatening	Same as Grade 3	Permanently discontinue dabrafenib and trametinib.

6.5.1.3.5 Mandatory dose modifications and recommended clinical management of serious skin reactions

Withhold trametinib for intolerable or severe skin toxicity. Resume trametinib at reduced doses in subjects with improvement or recovery from skin toxicity within 3 weeks. In cases of Stevens-Johnson syndrome and toxic epidermal necrolysis, permanently discontinue dabrafenib and trametinib and institute supportive care as per institutional guidelines.

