6.5.1.2 Other dose modifications and reductions

The following sections address the specific instructions for mandatory dose modifications and recommended management for AEs considered suspected to be related to study treatment. For subjects who do not tolerate the protocol-specified dosing schedule, dose interruptions or modifications are mandated in order to allow subjects to continue study treatment.

Three dose reductions for dabrafenib and two dose reductions for trametinib are permitted. If more dose reductions of dabrafenib and trametinib are required, the subject must be permanently discontinued from that specific study treatment. Dose modification steps for dabrafenib and trametinib in [Table 6-5](#) must be followed for the AEs presented in [Section 6.5.1](#).

Table 6-6 provides sections where detailed dose modification and management requirements for relevant AEs can be found. All AEs are to be graded according to NCI-CTCAE v4.03, unless otherwise specified. Investigators should refer to the current dabrafenib and trametinib local prescribing information for additional information regarding the background of each drug and the management of other AEs or potential safety-related issues not specifically mentioned in this protocol.

If treatment-related toxicities occur that are specific to combination treatment of dabrafenib and trametinib, then both treatments should be simultaneously dose reduced, interrupted or discontinued with the exceptions shown below:

Exception where dose modification is necessary for **only dabrafenib**:

- Uveitis (Table 6-18)

Exception where dose modifications are necessary for **only trametinib**:

- RVO (Table 6-18) and retinal pigment epithelial detachment (RPED) (Table 6-19)
- Left ventricular ejection fraction (LVEF) reduction (Table 6-15)

If a subject's dose of dabrafenib and trametinib has been reduced per the dose modification instructions, re-escalation of the subject's dose is recommended provided the following criteria are met:

- a period of 4 weeks of treatment has passed since restarting dosing at the lower dose level and there is no recurrence of the AE
- the subject is deriving clinical benefit

For dabrafenib and/or trametinib related adverse events: if following an interruption of dabrafenib and trametinib, an AE doesn't recover to \leq Grade 1 or baseline within 4 weeks, dabrafenib and trametinib must be discontinued.

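### An intolerable or severe rash can fall under two mandatory skin rules that differ on the drugs named, the restart criterion and the time condition

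*Protocol*

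**What the plan says.** Section 6.5.1.3.5 of the protocol covers serious skin reactions, and its heading describes the dose modifications as mandatory. It opens "Withhold trametinib for intolerable or severe skin toxicity" and continues "Resume trametinib at reduced doses in subjects with improvement or recovery from skin toxicity within 3 weeks". Dabrafenib appears only in the next sentence: "In cases of Stevens-Johnson syndrome and toxic epidermal necrolysis, permanently discontinue dabrafenib and trametinib". The section gives no grades and no cross-reference to the rash table.

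Section 6.5.1.3.4 covers skin rash, is also headed as mandatory, and works through Table 6-9, which grades rash by body surface area.

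- **Grade 2, intolerable.** The instruction starts "Interrupt, dabrafenib and trametinib until" (Grade 1 or lower) and goes on "and then reinstate reduce dabrafenib and trametinib to the next dose level".
- **Grade 3.** It starts "Interrupt dabrafenib and trametinib until" (again Grade 1 or lower), after which both drugs are reduced.
- **Time condition.** The Grade 2 entry requires that resolution to Grade 1 or "baseline must occur within a period of 4 weeks since a Grade 2 event has been identified". The first-occurrence entry for Grade 3 carries the same 4 weeks.

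Section 6.5.1.2 adds a general rule for related adverse events: if, after both drugs are interrupted, the event has not returned to Grade 1 or lower, or to baseline, within 4 weeks, both must be discontinued.

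**The concern.** An investigator facing an intolerable or severe rash can find two mandatory instructions and no statement of which governs. One names trametinib only and restarts it on improvement. The other stops both drugs and waits for Grade 1. Two sites could manage the same rash differently, each following a mandatory section.

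The statistical stake is in the descriptive safety outputs. SAP Section 5.4.1 summarises reductions, interruptions and permanent discontinuations, and dose intensity, separately for dabrafenib and trametinib. Permanent discontinuation for any adverse event by 12 months is a secondary endpoint (Protocol Table 2-1 and Section 12.5.2). The list in SAP Section 7.2 separates discontinuations of trametinib, of dabrafenib and of both, and adds a skin-toxicity table; the SAP's addendum leaves that section out of the final analysis. Whether one drug or both were stopped is the distinction that these outputs draw.

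**Working it through.** No arithmetic decides this point, so the two texts are set side by side.

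| Element | Section 6.5.1.3.5 | Table 6-9 |
|---|---|---|
| Trigger | Skin toxicity that is intolerable or severe, no grade | Rash: intolerable Grade 2 (10-30% of body surface) or Grade 3 (over 30%) |
| Drugs named | Trametinib; dabrafenib only for Stevens-Johnson syndrome and toxic epidermal necrolysis | Both |
| State needed before restart | Improvement or recovery, no grade | Grade 1 or lower (later Grade 3 occurrences add baseline) |
| Time condition | 3 weeks, start not stated | 4 weeks from identification of the event, under the first-occurrence entries |
| If not met | Not stated | Not stated in the table; Section 6.5.1.2 discontinues both |

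**Do the scopes overlap?** Four points in the documents say that they can.

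1. Intolerable is a trigger in both texts.
2. SAP Section 8.2 describes the CTCAE scale as generally running from mild and moderate through severe to life threatening and death, which puts severe at Grade 3. Protocol Section 10.1.1 uses the same order where no CTCAE grading exists.
3. Protocol Table 10-1 names rash as an example of a skin toxicity, and the SAP's table of adverse events of special interest repeats it.
4. Section 6.5.1.3.5 does not exclude rash.

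**Where do the instructions part?** Take a first Grade 3 rash in three courses, counting both periods from the same day for simplicity.

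- *Grade 1 by week 2.* Both texts withhold trametinib and resume it at a lower dose. Table 6-9 also interrupts and reduces dabrafenib; Section 6.5.1.3.5 gives no instruction for it.
- *Improved to Grade 2 by week 3.* Section 6.5.1.3.5 has trametinib resume at a reduced dose. Table 6-9 keeps both drugs off until Grade 1 or lower.
- *No improvement through week 3, Grade 1 in week 4.* Table 6-9 is satisfied and both drugs restart at a reduced level. The period in Section 6.5.1.3.5 has passed, and it does not say what follows.

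The nominal time difference is 4 - 3 = 1 week, or 7 days. It matters only in the third course; the restart criterion decides the second.

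The Amendment 2 log records the 4-week criterion being put into Table 6-9 and lists no change to Section 6.5.1.3.5. That may be how the two came apart, but it is inference. The difference itself lies between two current sections.

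**The case against.** The strongest reply is that the protocol treats these as separate events. Table 6-6 has one row for skin rash, pointing to Table 6-9, and another for serious skin reaction, pointing to Section 6.5.1.3.5. An investigator with a graded rash is routed to Table 6-9. Someone who stopped both drugs and waited for Grade 1 within 3 weeks would breach neither text. This stands in part: it makes Table 6-9 the natural first stop for an ordinary rash. It does not remove the overlap, because the operative sentence in Section 6.5.1.3.5 reaches skin toxicity generally, and the second course above leads to different actions.

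Four stronger readings are tempting, and the documents do not support them.

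- **That Section 6.5.1.3.5 directs dabrafenib to continue.** It is silent. That only trametinib is meant is the natural reading, since the section names both drugs where it means both. But where the protocol intends dabrafenib to continue it can say so, as in Table 6-10 for pneumonitis.
- **That Table 6-6 contradicts the section by marking both drugs.** Its footnote says only that a marked drug may need modifying, and Section 6.5.1.3.5 does stop both for the two named syndromes.
- **That the exceptions list in Section 6.5.1.2 proves the conflict.** That rule, "then both treatments should be simultaneously dose reduced, interrupted or discontinued with the exceptions shown below", concerns toxicities specific to the combination. Its list also omits pneumonitis (Table 6-10) and uncomplicated venous thromboembolism (Section 6.5.1.3.18), where only trametinib is interrupted.
- **That 3 weeks is a stopping deadline.** It is written as a condition for restarting, with no stated consequence.

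**Conclusion.** The inconsistency is real and bounded. An intolerable Grade 2 or a Grade 3 rash can come under two mandatory texts that differ on the drugs named, the restart criterion and the time condition. This rests on reading skin toxicity to include rash, as Table 10-1 does, and severe as Grade 3.

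The size is unknown. Neither document gives a count of intolerable Grade 2 or Grade 3 rash. Protocol Section 1.1.1.3 lists rash among events above 20% in the pooled metastatic studies, at any grade, and does not list it among Grade 3 or 4 events at 5% or more. That cannot be carried over to this population or to intolerable Grade 2 rash. A reader might infer that every such rash was handled inconsistently. The documents show only that such a rash can fall under both rules, and Table 6-6 would steer many to one of them.

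The primary endpoint counts pyrexia outcomes only (Protocol Section 12.4.1, SAP Section 5.5.1) and is not directly affected. The outputs exposed are single-arm descriptive summaries. The matter should be clarified for patient safety and for the meaning of the per-drug counts; it does not threaten the trial's main conclusion.

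**What to change.** Reconcile Section 6.5.1.3.5 with Section 6.5.1.3.4 and Table 6-9, and with the general 4-week rule in Section 6.5.1.2:

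- define which skin events each section covers, and say whether a rash can ever come under Section 6.5.1.3.5;
- for any event covered by both, state one set of drugs affected, one restart criterion, and one time limit with its starting point and the consequence of missing it;
- in Section 6.5.1.3.5, say explicitly what happens to dabrafenib outside the two named syndromes.

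Which rule should prevail is for the sponsor's clinical team; this review takes no position.

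The cost is a protocol clarification, with no change to sample size, analysis sets or methods. The SAP's cut-off dates imply that dosing in this trial is complete. If so, the text change matters mainly where the guidance is reused, and a sentence in the study report should say that drug-specific actions for rash were taken under two differing texts.

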6.5.1.3.6 Mandatory dose modifications and recommended clinical management guidelines for pneumonitis

Guidelines for dose modification and management of pneumonitis considered to be related to study treatment by the investigator are provided in [Table 6-10](#).

Table 6-10 Mandatory dose modifications and recommended clinical management guidelines for pneumonitis

Pneumonitis (NCI-CTCAE v4.03)		
Grade	Recommended adverse event management guidelines	Mandatory dose modification requirements
Grade 1: Radiographic changes only- Asymptomatic	
 CT scan (high-resolution with lung windows) recommended, with serial imaging to monitor for resolution or progression- re-image at least every 3 weeks Monitor for symptoms every 2-3 days - Clinical evaluation and laboratory work-up for infection Monitoring of oxygenation via pulse oximetry recommended Consultation of pulmonologist recommended. 	
 Continue dabrafenib and trametinib at the same dose.
Grade 2: Symptomatic- medical intervention indicated; limits instrumental ADLs	
 CT scan (high-resolution with lung windows) Monitor symptoms daily, consider hospitalization Clinical evaluation and laboratory work up for infection Consult pulmonologist Pulmonary function tests - if normal at baseline, repeat every 8 weeks Bronchoscopy with biopsy and/or BAL recommended 	
 Interrupt trametinib until recovery to ≤ Grade 1 or baseline. Dabrafenib may continue at the same dose. Once recovered, reduce trametinib to the next lower dose per Table 6-5. Re-escalation of the subject's dose is recommended if criteria in Section 6.5.1.2 are met. If no recovery to ≤ Grade 1 within 4 weeks, permanently discontinue trametinib. Dabrafenib may continue. AE resolution to ≤ Grade 1 or baseline must occur within a period of 4

Pneumonitis (NCI-CTCAE v4.03)		
Grade	Recommended adverse event management guidelines	Mandatory dose modification requirements
	
 • Symptomatic therapy including corticosteroids if clinically indicated (systemic corticosteroids at a dose of 1 to 2 mg/kg/day prednisone or equivalent as clinically indicated). 	
weeks since Grade 2 event has been identified.

Grade 3: Severe symptoms; limits self-care ADLs; oxygen indicated	
 • CT scan (high-resolution with lung windows) • Clinical evaluation and laboratory work-up for infection • Consult pulmonologist • Pulmonary function tests-if < normal, repeat every 8 weeks until \geq normal • Bronchoscopy with biopsy and/or BAL if possible • Treat with intravenous steroids (methylprednisolone 125 mg) as indicated. When symptoms improve to \leq Grade 1, a high dose oral steroid (prednisone 1 to 2 mg/kg once per day or dexamethasone 4 mg every 4 hours). • If IV steroids followed by high dose oral steroids does not reduce initial symptoms within 48 to 72 hours, consider non-corticosteroid immunosuppressive medication (e.g., infliximab, cyclophosphamide, IVIG or mycophenolate mofetil). 	
 • Interrupt trametinib until recovery to Grade \leq1 or baseline. Dabrafenib may continue. • Once recovered, trametinib may be restarted at the next lower dose per Table 6-5. Re-escalation of the subject's dose is recommended if criteria in Section 6.5.1.2 are met • If no recovery to Grade \leq 1 or baseline within 4 weeks, permanently discontinue trametinib. Dabrafenib may continue.
Grade 4: Life-threatening respiratory compromise	Same as Grade 3	Same as Grade 3

6.5.1.3.7 Dose modification and management guideline for adverse events suspected to be related to dabrafenib and/or trametinib (other than Pyrexia)

For adverse events of special interest reported **only for dabrafenib and/or trametinib**, general guidelines for dose modification in [Table 6-11](#) should be followed for dabrafenib and trametinib.

In general, if an AE resolves to Grade 1 or baseline at the reduced dose level, and no additional toxicities are seen after 4 weeks of study treatment at the reduced dose, the dose may be increased to the previous dose level.

A dose reduction below 50 mg BID for dabrafenib or below 1 mg QD for trametinib is not allowed. If a dose reduction below 50 mg BID for dabrafenib is required, dabrafenib will be permanently discontinued but these subjects will be allowed to continue trametinib. If a dose reduction below 1.0 mg QD for trametinib is required, then trametinib will be permanently discontinued, but these subjects will be allowed to continue dabrafenib.

Table 6-11 General guidelines for dose modification for adverse events suspected to be related to dabrafenib and/or trametinib treatment

Grade	Recommended adverse event management guidelines	Mandatory dose modification requirements
Grade 1 or Grade 2 tolerable	
 • Monitor closely. • Provide supportive care according to institutional standards. 	
 • Continue dabrafenib and trametinib at the same dose level.
Grade 2 (intolerable) or Grade 3	
 • Monitor closely. • Provide supportive care according to institutional standards. 	
 • Interrupt dabrafenib and trametinib (except for cuSCC, keratoacanthoma, new primary melanoma, and basal cell carcinoma) • When toxicity resolves to ≤ Grade 1 or baseline, restart dabrafenib and trametinib reduced by one dose level per Table 6-5. Re-escalation of the subject's dose is recommended if criteria in Section 6.5.1.2 are met • If the Grade 2 (intolerable) or Grade 3 toxicity recurs, interrupt dabrafenib and trametinib. • When toxicity resolves to Grade 1 or baseline, restart dabrafenib and trametinib reduced by another dose level per Table 6-5. Re-escalation of the subject's dose is recommended if criteria in Section 6.5.1.2 are met

Grade	Recommended adverse event management guidelines	Mandatory dose modification requirements
Grade 4	
 • Monitor closely. • Provide supportive care according to institutional standards. 	
 • Interrupt dabrafenib and trametinib. • Restart with dabrafenib and trametinib reduced by one dose level per Table 6-5 once toxicity resolves to \leq Grade 1 or baseline or permanently discontinue dabrafenib and trametinib at the discretion of the investigator. Re-escalation of the subject's dose is recommended if criteria in Section 6.5.1.2 are met

6.5.1.3.8 Mandatory dose modifications and recommended clinical management guidelines for hand-foot reaction (palmar-plantar erythrodysesthesia)

In general, management of hand-foot skin reactions include:

- Prevention/prophylaxis: promote sunscreen use and avoidance of unnecessary sun exposure, use alcohol-free emollient creams, topical steroids and antibiotics as needed.
- Pruritic lesions: cool compresses and oral antihistamines
- Fissuring lesions: Monsel's solution, silver nitrate or zinc oxide cream
- Desquamation: thick emollients and mild soap
- Paronychia: antiseptic bath, local potent corticosteroids, antibiotics, surgery as needed
- Infected lesions: topical or systemic antibiotics
- Measures for PPES should include:
 - Lifestyle modification: avoidance of hot water, traumatic activity, constrictive footwear, or excessive friction on the skin and the use of thick cotton socks and gloves, and shoes with padded insoles
 - Symptomatic treatments: apply moisturizing creams frequently, topical keratolytics (e.g., urea 20-40% cream, salicylic acid 6%, tazarotene 0.1% cream, fluorouracil 5% cream), clobetasol propionate 0.05% ointment for erythematous areas, topical lidocaine 2%, and / or systemic pain medication such as nonsteroidal anti-inflammatory drugs, codeine, and pregabalin for pain.

Guidelines for dose modification for hand-foot skin reaction considered to be related to study treatment by the investigator are provided in [Table 6-12](#).

Table 6-12 Mandatory dose modifications and recommended clinical management guidelines for hand foot skin reaction (palmar-plantar erythrodysesthesia)

Hand foot skin reaction		
Grade	Recommended adverse event management guidelines	Mandatory dose modification requirements
Grade 1: Numbness, dysesthesia, paresthesia, tingling, painless swelling, erythema or discomfort of the hands or feet which does not disrupt the subject's normal activities	
 Recommend topical therapy for symptomatic relief. 	
 Continue dabrafenib and trametinib at the same dose.
Grade 2: Painful erythema and swelling of the hands or feet and/or discomfort affecting the subject's normal activities	
 Recommend topical therapy for symptomatic relief 	
 Continue treatment and if no improvement within 7 days, see below. No improvement within 7 days or 2nd or 3rd occurrence: Interrupt dabrafenib and trametinib until toxicity resolves to ≤ Grade 1 or baseline. Reduce dabrafenib and trametinib at the next lower dose per Table 6-5. Re-escalation of the subject's dose is recommended if criteria in Section 6.5.1.2 are met 
4th occurrence:
 
 Discontinue dabrafenib and trametinib.
Grade 3: Moist desquamation, ulceration, blistering or severe pain of the hands or feet, or severe discomfort that causes the subject to be unable to work or perform activities of daily living	
 Recommend topical therapy for symptomatic relief 	
1st occurrence:
 
 Interrupt dabrafenib and trametinib until toxicity resolves to ≤ Grade 1 or baseline. Once recovered, reduce dabrafenib and trametinib to the next dose level per Table 6-5. Re-escalation of the subject's dose is recommended if criteria in Section 6.5.1.2 are met 
2nd occurrence:
 
 Interrupt dabrafenib and trametinib until toxicity recovers to ≤ Grade 1 or baseline. Once recovered, reduce dabrafenib and trametinib to the next dose level per Table 6-5. Re-escalation of the subject's dose is recommended if criteria in Section 6.5.1.2 are met 
3rd occurrence:
 
 Discontinue dabrafenib and trametinib.

6.5.1.3.9 Mandatory dose modifications and recommended clinical management guidelines for hematological adverse events

Guidelines for dose modification for hematologic adverse events suspected to be related to study treatment by the investigator are provided in [Table 6-13](#).

Table 6-13 Mandatory dose modifications and recommended clinical management guidelines for hematological adverse events

Hematologic suspected AEs (NCI-CTCAE v4.03)		
Grade	Recommended adverse event management guidelines	Mandatory dose modification requirements
Neutropenia		
Grade 1, 2	NA	
 Continue dabrafenib and trametinib at the same dose.
Grade 3, 4	
 Monitor blood test more frequently (every 7 days for Grade 3, and 3-5 days for Grade 4). 	
1st occurrence:
 
 Interrupt dabrafenib and trametinib until toxicity recovers to \leq Grade 2 or baseline. Reduce dabrafenib and trametinib to the next dose level per Table 6-5. Re-escalation of the subject's dose is recommended if criteria in Section 6.5.1.2 are met 
2nd occurrence:
 
 Interrupt dabrafenib and trametinib until toxicity recovers to \leq Grade 2 or baseline. Reduce dabrafenib and trametinib at the next dose level per Table 6-5. Re-escalation of the subject's dose is recommended if criteria in Section 6.5.1.2 are met 
3rd occurrence:
 
 Interrupt dabrafenib and trametinib until toxicity recovers to \leq Grade 2 or baseline. Once recovered, reduce dabrafenib and trametinib to the next dose level per Table 6-5. Re-escalation of the subject's dose is recommended if criteria in Section 6.5.1.2 are met 
4th occurrence:
 
 Permanently discontinue dabrafenib and trametinib
Febrile Neutropenia	
 Apply Institutional guidelines 	
 Follow modification guide for neutropenia Grade 4 (above).
Thrombocytopenia		
Grade 1, 2, 3 without clinically significant bleeding	
 Grade 3: monitor blood test more frequently (every 7 days) 	
 Continue dabrafenib and trametinib at the same dose.

Hematologic suspected AEs (NCI-CTCAE v4.03)		
Grade	Recommended adverse event management guidelines	Mandatory dose modification requirements
Grade 3 with clinically significant bleeding Grade 4	
 Grade 3: monitoring blood test more frequently (every 3-5 days) 	
1st occurrence:
 
 Interrupt dabrafenib and trametinib until toxicity resolves to ≤ Grade 2 or baseline. Restart dabrafenib and trametinib at same dose. 
2nd occurrence:
 
 Interrupt dabrafenib and trametinib until toxicity resolves to ≤ Grade 2 or baseline. Restart dabrafenib and trametinib at the next lower dose per Table 6-5. Re-escalation of the subject's dose is recommended if criteria in Section 6.5.1.2 are met 
3rd occurrence:
 
 Interrupt dabrafenib and trametinib until toxicity resolves to ≤ Grade 2 or baseline. Restart dabrafenib and trametinib at another lower dose per Table 6-5. Re-escalation of the subject's dose is recommended if criteria in Section 6.5.1.2 are met 
4th occurrence:
 
 Interrupt dabrafenib and trametinib until toxicity resolves to ≤ Grade 2 or baseline. Permanently discontinue dabrafenib and trametinib.

6.5.1.3.10 Mandatory dose modifications and recommended clinical management guidelines for non-hematological adverse events

Guidelines for dose modification for non-hematologic adverse events suspected to be related to study treatment by the investigator are provided in [Table 6-14](#).

Table 6-14 Mandatory dose modifications and recommended clinical management guidelines for non-hematological adverse events

Non-Hematologic AEs (except Grade 2 alopecia, Grade 2 fatigue) (NCI-CTCAE v4.03)		
Grade	Recommended adverse event management guidelines	Mandatory dose modification requirements
Grade 1-2 tolerable	
 Monitor closely. Provide supportive care according to institutional standards. 	
 Continue, dabrafenib and trametinib at the same dose.
Grade 2 intolerable or Grade 3	
 Monitor closely Provide supportive care according to institutional standards 	
1st or 2nd occurrence:
 
 Interrupt dabrafenib and trametinib until toxicity recovers to ≤ Grade 1 or baseline. Restart dabrafenib and trametinib at the same dose. 
3rd occurrence:
 
 Restart dabrafenib and trametinib at the next lower dose per Table 6-5. Re-escalation of the subject's dose is recommended if criteria in Section 6.5.1.2 are met 
4th occurrence:
 
 Permanently discontinue dabrafenib and trametinib.
Grade 4	
Monitor closely
 
Provide supportive care according to institutional standards
	
1st occurrence:
 
 Interrupt dabrafenib and trametinib. Dabrafenib and trametinib may be reinitiated at the next lower dose per Table 6-5. Re-escalation of the subject's dose is recommended if criteria in Section 6.5.1.2 are met 
2nd occurrence:
 
 Permanently discontinue dabrafenib and trametinib.

6.5.1.3.11 Mandatory dose modification and management guideline for changes in LVEF suspected to be related to dabrafenib and/or trametinib treatment

Decreases of left-ventricular-ejection-fraction (LVEF) have been observed in patients receiving trametinib in combination with dabrafenib. Therefore, ECHOs must be performed to assess cardiac ejection fraction in regular intervals as outlined in the Visit Evaluation Schedule ([Table 8-1](#)). Dose modification guidance and stopping criteria for LVEF decrease are provided in [Table 6-15](#).

Table 6-15 Mandatory dose modification and recommended clinical management for changes in LVEF suspected to be related to dabrafenib and/or trametinib treatment

Left Ventricular Ejection Fraction decrease (NCI-CTCAE v4.03)		
LVEF-drop (%) & clinical symptoms	Recommended adverse event management guidelines	Mandatory dose modification requirements
Asymptomatic: Absolute decrease of >10% in LVEF compared to baseline and ejection fraction below the institution's LLN	
 Report as SAE. Closely monitoring LVEF via ECHO, repeat ECHO within 2 weeks*. If the LVEF recovers within 4 weeks (defined as LVEF \geqLLN and absolute decrease \leq10% compared to baseline) 
 Repeat ECHO 2, 4, 8 and 12 weeks after re-start; continue in intervals of 12 weeks thereafter. If repeat LVEF does not recover within 4 weeks. 
 Consult with cardiologist Repeat ECHO after 2, 4, 8, 12, and 16 weeks or until resolution 	
 Interrupt trametinib. If the LVEF recovers, restart trametinib reduced by one dose level per Table 6-5. More than two occurrence, permanently discontinue trametinib. Permanently discontinue trametinib if repeat LVEF does not recover within 4 weeks.
Symptomatic: Resting LVEF 39-20% or >20% absolute reduction from baseline resting LVEF <20%	
 Report as SAE. Consult with cardiologist. Repeat ECHO after 2, 4, 8, 12, and 16 weeks or until resolution. 	
 Permanently discontinue trametinib. Interrupt dabrafenib Restart dabrafenib if LVEF recovers including resolution of symptoms.

* If ECHO does not show LVEF recovery after 2 weeks, repeat ECHO 2 weeks later.

6.5.1.3.12 Mandatory dose modification and management guideline for hypertension suspected to be related to dabrafenib and/or trametinib treatment

Increases in blood pressure have been observed in patients receiving trametinib. For adequate monitoring and management of hypertension, all blood pressure assessments should be performed under the following optimal conditions:

- the subject has been seated with back support, ensuring that legs are uncrossed and flat on the floor
- the subject is relaxed comfortably for at least 5 minutes
- restrictive clothing has been removed from the cuff area and the right cuff size has been selected
- the subject's arm is supported so that the middle of the cuff is at heart level
- the subject remains quiet during the measurement.

In subjects with an initial blood pressure reading within the hypertensive range, a second reading should be taken at least 1 minute later, with the 2 readings averaged to obtain a final blood pressure measurement. The averaged value should be recorded in the eCRF.

Persistent hypertension is defined as an increase of systolic blood pressure (SBP) > 140 mm Hg and/or diastolic blood pressure (DBP) > 90 mm Hg in three consecutive visits with blood pressure assessments from two readings collected as described above. Visits to monitor

increased blood pressure can be scheduled independently from the per- protocol visits outlined in the Visit Evaluation Schedule ([Table 8-1](#)). Ideally, subsequent blood pressure assessments should be performed within one week.

Asymptomatic hypertension is defined as an increase of SBP >140 mm Hg and/or DBP >90 mmHg in the absence of headache, light-headedness, vertigo, tinnitus, episodes of fainting or other symptoms indicative of hypertension.

For subjects experiencing an increase in systolic and/or diastolic blood pressure that is persistent and may be associated with the study treatment, recommendations for dose modifications and management of hypertension are described below in [Table 6-16](#).

Table 6-16 Mandatory dose modification and recommended clinical management for hypertension suspected to be related to dabrafenib and/or trametinib treatment

Hypertension (NCI-CTCAE 4.03)		
Severity	Recommended adverse event management guidelines	Mandatory dose modification requirements
(Scenario A) Asymptomatic and persistent ^a SBP of >140 and <160 mmHg, or DBP >90 and <100 mmHg, or Clinically significant increase in DBP of 20 mmHg (but still below 100 mmHg).	
 Adjust current or initiate new antihypertensive medication. Titrate antihypertensive medication(s) during the next 2 weeks as indicated to achieve well-controlled BP^b If BP is not well controlled within 2 weeks, recommended to refer to a specialist and go to scenario (B). 	Continue dabrafenib and trametinib at the same dose.
(Scenario B) Asymptomatic SBP ≥160 mmHg, or DBP ≥100 mmHg, or Failure to achieve well-controlled BP within 2 weeks in Scenario A	
 Adjust current or initiate new antihypertensive medication(s). Titrate antihypertensive medication(s) during the next 2 weeks as indicated to achieve well-controlled BP. 	
 Interrupt dabrafenib and trametinib if clinically indicated. Once BP is well controlled, restart dabrafenib and trametinib reduced by one dose level per Table 6-5.
Symptomatic ^c hypertension or Persistent SBP ≥160 mmHg, or DBP ≥100 mmHg, despite antihypertensive medication and dose reduction of study treatment.	
 Adjust current or initiate new antihypertensive medication(s) Titrate antihypertensive medication during the next 2 weeks as indicated to achieve well-controlled BP. Referral to a specialist for further evaluation and follow-up is recommended 	
 Interrupt dabrafenib and trametinib. Once BP is well controlled, restart dabrafenib and trametinib reduced by one dose level per Table 6-5.
Refractory hypertension unresponsive to above interventions or hypertensive crisis.	
 Continue follow-up per protocol. 	
 Permanently discontinue dabrafenib and trametinib.

a. Hypertension detected in two separate readings during up to three consecutive visits.
b. Well-controlled blood pressure defined as SBP ≤140 mm Hg and DBP ≤90 mm Hg in two separate readings during up to three consecutive visits.
c. Symptomatic hypertension defined as hypertension aggravated by symptoms (e.g., headache, light-headedness, vertigo, tinnitus, episodes of fainting) that resolve after the blood pressure is controlled within the normal range.

6.5.1.3.13 Mandatory dose modifications and recommended clinical management guidelines for diarrhea/colitis

Guidelines for dose modification and management for diarrhea considered to be related to study treatment by the investigator are provided in [Table 6-17](#).

Table 6-17 Mandatory dose modifications and recommended clinical management guidelines for diarrhea/colitis

CTCAE v4.03	Recommended adverse event management guidelines	Mandatory dose modification requirements

Grade 1 diarrhea (increase of <4 stools per day over baseline; mild increase in ostomy output compared to baseline) OR Grade 2 diarrhea (increase of 4 - 6 stools per day over baseline; moderate increase in ostomy output compared to baseline)
	
 • Diet: stop all lactose containing products; eat small meals, BRAT diet (banana, rice, apples, toast) • Hydration: 8-10 large glasses of clear liquids per day (e.g., Gatorade or broth) • Loperamide: initially 4 mg, followed by 2 mg every four hours or after every unformed stool; maximum 16 mg/day. Continue until diarrhea free for 12 hours; • Diarrhea > 24hr: loperamide 2 mg every two hours; maximum 16 mg/day. Consider adding oral antibiotics. • Diarrhea > 48hr: loperamide 2 mg every two hours; maximum 16 mg/day. Consider other second-line therapies for diarrhea (e.g., octreotide, oral diphenoxylate, and oral antibiotics) • If Grade 2 and no improvement in 5 days consider oral steroids • If Grade 2 diarrhea persists >1 week consider gastroenterologist consultation and endoscopy to evaluate for colitis • If Grade 2 persists for 5 days and worsening of symptoms or diffuse ulcerations and bleeding seen on endoscopy, commence oral steroids at a dose 0.5 to 1 mg/kg/day prednisone equivalents and continue until symptoms improve to Grade 1. If no improvement occurs, manage as per Grade 3. • Lower GI endoscopy and biopsy should be considered and may assist in determining the duration of steroid taper based on the evidence of macroscopic and microscopic inflammation. 	
 • Continue dabrafenib and trametinib at the same dose level. • If diarrhea is Grade 2, despite loperamide at 2 mg every two hours for > 48hr: 
 • Interrupt dabrafenib and trametinib until ≤ Grade 1, and then reinstate, dabrafenib and trametinib at the same dose level.

Grade 3 diarrhea (increase of ≥7 stools per day over baseline; incontinence; hospitalization indicated; severe increase in ostomy output compared to baseline; limiting self-care ADL)
	
 • Clinical evaluation and hospitalization mandatory; rule out bowel perforation and intravenous hydration. • Consider consultation with gastroenterologist and 	
1st occurrence
 
 • Interrupt, dabrafenib and trametinib until ≤ Grade 1, and then reinstate treatment (after appropriate steroid tapering) and reduce dabrafenib and trametinib to the next lower dose level per Table 6-

CTCAE v4.03	Recommended adverse event management guidelines	Mandatory dose modification requirements
